2.2.2 Secondary Endpoints

Tolerability - 75% of patients will be able to tolerate trial medication, in at least half dose, up to one year after randomisation (i.e. less than 25% will stop trial medication completely through inability to tolerate the drugs).

Safety - symptoms of systemic or intracranial bleeding, recurrent cerebral and systemic vascular events, and vascular and non-vascular causes of death will be collected. The absolute risk of death, including fatal haemorrhage, will not differ significantly (ie fall outside the upper 95% CI) from 2% per year on trial drugs versus no trial drugs, when given in addition to guideline drugs; and will not increase bleeding or ischaemic SVD lesions significantly (at the p<0.01 level) on MRI.

Efficacy – individual event-rate data (stroke, TIA, myocardial ischaemia, cognitive impairment and dementia, will be collected. The *combined rate* of recurrent stroke, MI, death, cognitive impairment and dependency will be 40-50% at one year after enrolment in order to detect modest but clinically-important reductions in poor outcomes.

Health Economics – data to assess health economic impact will be gathered.

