9 STATISTICS AND DATA ANALYSIS

9.1 SAMPLE SIZE CALCULATION

There are few data on which to base sample size. There is little experience with cilostazol in Europe or North America, and little experience with ISMN in this group of patients in the UK (or in any patients with stroke). We have been guided by colleagues in Japan where cilostazol is in common use and there is experience with it in stroke. The main purposes of the trial are to assess tolerability and safety.

Table 6 Annual absolute risks (%) of outcome events after lacunar stroke

Vascular death	Non-vasc death	Non-fatal isch stroke or TIA	Non-fatal ICH	MI	MACE	Dependent (mRS 3-5)	Any cogn impt.	Dementia
1.8	0.5	2.5	0.5	0.6	3	15	30	15

We calculated mean annual event rates (Table 6) from trials (SPS3,³³ lacunar patients in ENOS⁵⁰ IST-3,⁶³ of cilostazol, Figure 1) and observational data (LADIS;⁶⁴ our^{4, 65} and other⁶⁶

studies). We expect deaths including vascular deaths of median 2.0% p.a., with 4% being the upper 95% CI of 2% in 400 patients.³³ LACI-2 therefore has a sample size of 400.

For a main Phase III trial, recurrent stroke 2.5%pa, MI 0.6%pa and vascular death 1.8%pa,^{4, 33} (MACE) are infrequent; new cognitive impairment c16% at one year,^{6, 66} dependency 15%, are frequent and important to patients, justifying their inclusion in a composite primary outcome. However, these event rates are imprecise with wide ranges; more precise estimates are needed. We estimate main Phase III trial sample size at 1100 (Table 7), assuming 80% power, alpha 5%, 10% loss to follow-up, composite event rate (45%) and conservative estimate of cilostazol effect (20% RRR is the lower 95% CI of effect, Figure 1). A primary outcome including MRI SVD progression (A, below) was considered but at least 15% of patients miss repeat MRI, sample sizes were similar (or larger, due to variance in WMH change⁶⁵ short term), the cost is much higher and the WMH intermediary measure is less relevant to patients.

Table 7. Sample size for composite outcome in main trial, estimated event rates.

Composite model	A	B	Ci	Cii	D
Composite outcome for Phase III includes:	MACE, dementia, non-vasc death, new MR signs	MACE, dementia, death	MACE, cog↓, dependency↓, death		MACE, cog imp, depend, all death
1-beta (power)	80%	80%	80%	80%	80%
Event rate, control, pa	50%	10%	30%	30%	45%
Relative risk reduction	20%	20%	20%	30%	20%
Event rate, active, pa	40%	8%	24%	21%	36%
Total sample size	950	6626	1784	778	976

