SUPPLEMENT – LACunar Intervention Trial 2 (LACI-2) Statistical Analysis Plan

SECTION 1. ADMINISTRATIVE INFORMATION

1 Title and trial registration

1a Title: Lacunar Intervention Trial 2

Acronym: LACI-2

1b Registration: ISRCTN14911850; IRAS project number: 206480

2 SAP version: 1.5 (06 June 2022)

3 Protocol version: 7.0 (14 October 2020)

4 SAP revisions

4a Revision history:

Version 1.4 to 1.5

- Text added about the planned soft database lock and analysis (section 13a).
- Text added explaining comparison of dual versus no treatment (section 27a).
- Differences and p values removed (Tables 1, 5).
- Analyses comparing dual versus no treatment do not include all four groups so cilostazol only and ISMN groups removed (Table 9).

4b Justification for each revision: N/A

4c Timing of SAP revisions: These antedate data lock and analysis. Where there is a difference between the protocol (on website), published protocol ¹ and SAP, the SAP will take precedence.

5 Roles and responsibilities

Author: [name]

Responsible statisticians: [name] (blinded statistician), [name] (blinded statistician), [name]

Chief Investigator: [name]

Contributors and roles:

[name], [name], [name], [name], [name], [name], [name], for the LACI-2 Investigators*

6 Signatures

Role	Name	Signature	Date
6a Author:	[name]	 [name] (Jun 9, 2022 10:02 GMT+1)	Jun 9, 2022
6b Senior statistician	[name]		Jun 15, 2022
6c Chief Investigator:	[name]		Jun 9, 2022

SECTION 2. INTRODUCTION

7 Background and rationale

Prior to analysis and presentation of the primary results, this publication presents the statistical analysis plan (SAP)^{2 3} alongside the detailed listing of baseline characteristics presented in the accompanying baseline paper. This Supporting Information Appendix S1 details the full SAP and is presented prior to locking of the study database so that analyses are not data driven or reported selectively.⁴ In addition to the SAP, we also list planned secondary analyses and substudies. The SAP follows the recommended layout.^{2 3}

8 Objectives

8a Primary Objective: To determine whether a prospective, randomised trial of cilostazol and ISMN, individually or in combination, on a background of guideline stroke prevention therapy, in lacunar ischaemic stroke is feasible in the UK, thence proceeding as seamlessly as possible to a large phase III trial.

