8b Secondary Objectives: To assess drug tolerability, safety, recruitment rates and accuracy, outcome event rates and retention in preparation to a large phase III randomised controlled trial to prevent recurrent lacunar stroke and physical and cognitive impairment.

This SAP focuses on these primary and secondary objectives. Planned follow-on publications will address tertiary questions.

SECTION 3. STUDY METHODS

9 Trial design

Prospective randomised open-label blinded end-point (PROBE) partial-factorial phase IIb/c trial aiming to recruit 400 patients recruited in UK Stroke Network Centres, with follow-up to one year.

10 Randomisation: By central computer-generated allocation at the University of Nottingham with minimisation on key prognostic factors: age, sex, stroke severity (NIHSS), dependency resulting from the stroke, systolic blood pressure $\leq/ > 140$ mmHg, smoking status, time after stroke, and years of education.

11 Sample size/power considerations

Conservatively, we have used sample size calculations based on binary measures. Use of ordinal measures at the time of analysis will increase statistical power.

11a Event rates: Annual event rates (Table A) were assessed from trials (SPS3,⁵ lacunar patients in ENOS,^{6 7} IST-3^{8 9}) and observational data (LADIS;¹⁰ our¹¹⁻¹³ and other¹⁴ studies). All-cause death rates were assumed to be 2.0% with upper 95% CI of 4% in 400 patients.⁵ Hence, the sample size was set at 400 participants.

Table A Annual absolute risks (%) of outcome events after lacunar stroke

Vascular death	Non-vascular death	Non-fatal IS or TIA	Non-fatal ICH	MI	MACE	Dependent (mRS 3-5)	Cognitive impairment	Dementia
1.8	0.5	2.5	0.5	0.6	3	15	30	15

ICH: intracerebral haemorrhage; IS: ischaemic stroke; MACE: major adverse cardiac events; MI: myocardial infarction; mRS: modified Rankin scale; TIA: transient ischaemic stroke

11b Comparison of two groups in a future phase III trial: Assuming power 0.80, alpha=0.05, 1:1 randomisation, composite event rate (MACE, dementia, non-vascular death, new MRI signs) 45% and absolute reduction 9% (relative risk reduction 20%), and loss to follow-up 10%, a sample size of 1100 will be needed. A

number of outcomes are relevant to patients with SVD and using these has implications for the sample size (Table B).

Table B. Sample size for composite outcome in main trial using estimated event rates.¹

Composite model	A	B	Ci	Cil	D

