Composite outcome for phase III	MACE, dementia, non-vascular death, new MR signs	MACE, dementia, death	MACE, cognitive decline, dependency decline, all-cause death		MACE, cognitive impairment, dependency, all-cause death
1-beta (power)	80%	80%	80%	80%	80%
Event rate, control, pa	50%	10%	30%	30%	45%
Relative risk reduction	20%	20%	20%	30%	20%
Event rate, active, pa	40%	8%	24%	21%	36%
Total sample size	950	6626	1784	778	976
Total trial size, including losses	1250	7400	2000	900	1100

MACE: major adverse cardiac events; MRI: magnetic resonance imaging

12 Framework

The primary objectives are to assess the feasibility of recruitment and adherence to medication.

13 Statistical interim analyses and stopping guidance

13a Interim analyses: Data are tabulated twice annually prior to Trial Steering Committee (TSC) and Data Monitoring Committee (DMC) meetings. No unblinded comparative analyses will be performed until data collection has been completed and the database locked.

Prior to the final database lock, the database will be subject to a soft lock and the provisional data tabulated and analysed for review by the TSC and DMC. Any final queries will be raised and resolved prior to final database lock. Members of staff still involved in the collation of data and resolution of data queries will not attend the meeting and the data reviewed at the meeting will remain strictly confidential until the point of final database lock to avoid any bias.

13b Adjustments of significance level: There is no planned adjustment.

13c Stopping rules: There are no formal stopping rules, but the DMC have responsibility to make recommendations to pause or modify the study, should there be any safety or efficacy considerations.

14 Timing of final analyses

These will be performed once data collection has been completed and the database has been locked.

15 Timing of outcome assessments

Assessments will be performed at baseline, 1-2 weeks, 3-4 weeks, 6 and 12 months (**Table C**).

Table C. Assessments at baseline and follow-up by time point (adapted from protocol and ¹).

Assessment	Prior to Baseline	Visit 1 Baseline	Week 1-2	Week 3-4	Month 6	Month 12
Screening for eligibility and consent [†]	X ^s					
Confirm and document ongoing consent		X ^s				
Medical including drug history		X ^s				
Assess MR or CT diagnostic scan; send copy to Edinburgh		X ^s				
Randomisation		X ^s				

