- Recruitment of sufficient patients, i.e. 400 patients in 24 months in the UK (and taking account of interruption due to COVID-19).
- >95% of randomised patients are retained for follow-up at one year.

Secondary outcomes - participant

Tolerability: 75% of patients will be able to tolerate trial medication, in at least half dose, up to one year after randomisation (i.e. less than 25% will stop trial medication completely through inability to tolerate the drugs).

Safety

- Symptoms of systemic or intracranial bleeding.
- The absolute risk of death, including fatal haemorrhage, does not differ significantly, i.e. fall outside the upper 95% CI of 2% per year on trial drugs versus no trial drugs, when given in addition to guideline stroke prevention drugs.
- There are no new ischaemic or haemorrhagic brain lesions or increase in SVD lesions on one year MRI significantly (at the p<0.01 level).

Efficacy

- Individual event-rates for stroke, TIA, myocardial ischaemia, cognitive impairment and dementia.
- The *combined rate* of recurrent stroke, MI, death, mild cognitive impairment (including dementia), dependency and new stroke lesions on scanning at 1 year will be 40-50% at one year after enrolment in order to allow detection of a modest but clinically-important reduction in poor outcomes in a phase III trial.
- Health economic measures include the health utility score (EQ-5D-5L) and the visual analogue score (EQVAS) at 12 months.

26b Units: Units will be shown in tables.

26c Calculations/transformations: Quality of life using UK weightings.

Brain frailty

Based on neuroimaging:

- Brain frailty = Atrophy + WML + Previous stroke lesion ⁷

- SVD score for CT = WML, lacunes; for MRI includes WMH, lacunes, PVS and microbleeds ¹⁵

Montreal cognitive assessment-modified (MoCA-m) trails

Since Trails A and B are performed, the MoCA trail is not collected but rather estimated from the Trails B score:

- If Trails B score <12 then MoCA trail = 0
- If Trails B score >=12 then MoCA trail = 1

27 Analysis methods

27a Methods

Primary endpoint

- Tabulation and graphical presentation of participant recruitment aiming for 400 participants in 24 months.
- Tabulation of retention of participants at one year aiming for >95%.

Analyses of secondary outcomes

Tabulations of:

- Tolerability to trial medications aiming for 75% of patients taking at least half dose for up to one year after randomisation.

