- Death, including fatal haemorrhage, aiming for less than outside the upper 95% CI of 2% per year.
- The *combined rate* of recurrent stroke, MI, death, cognitive impairment and dependency, aiming for 40-50% at one year after enrolment.

Comparison of rates of events between the treatment groups: cilostazol vs no cilostazol, ISMN vs no ISMN, and cilostazol and ISMN vs neither, for:

- Systemic or intracranial bleeding, recurrent cerebral and systemic vascular events, and vascular and non-vascular causes of death.
- Death, all cause.
- New ischaemic or haemorrhagic stroke lesion or increase in SVD lesions on MRI.
- Composite of: recurrent clinically-evident stroke, MI, death, cognitive impairment (including dementia) and dependency.
- Individual event: stroke (clinically-evident or imaging-detected ischaemic or haemorrhagic stroke to be reported separately), TIA, myocardial ischaemia, cognitive impairment and dementia.
- New infarcts and haemorrhages, absolute and change in WMH, microhaemorrhages, lacunes, atrophy imaging variables from central read of baseline imaging and one year MRI
- The comparisons of combined cilostazol and ISMN versus neither, whilst being very underpowered statistically, are presented since these may be the two groups studied in the planned follow-on trial.

Central tendency, comparisons and regressions will be analysed as follows (**Table D**).

Table D. Descriptive and analytical statistics

	Binary	Nominal	Ordinal	Continuous
Central tendency and distribution	N (%)	N (%)	Median [interquartile range]	Mean (standard deviation)
Comparisons	Chi-square (2x2)	Chi-square (2x2, or rxc)	Mann-Whitney U or Kruskal-Wallis	t-test (pooled) or 1-way ANOVA
Regression	Binary logistic regression (BLR)	-	Ordinal logistic regression (OLR)	Multiple linear regression (MLR)

27b Covariate adjustment: Analyses will be adjusted for minimisation covariates:

- Age, sex, stroke severity (NIHSS), dependency resulting from the stroke, systolic blood pressure, smoking status, time after stroke, years of education.

Covariate adjustment with continuous variables (age, NIHSS, SBP, time after stroke, years of education) will use original, not dichotomised, data.

27c Assumption checking: The assumption of proportionality will be tested using the likelihood test.

27d Alternative methods: If the data fail the assumption of proportionality (tested using the likelihood test), we will use alternative methods such as multiple logistic regression.

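### SAP Table 2 sets the death metric at <2%, while SAP 26a and 27a judge death against the upper 95% confidence limit of 2% (4% in 400 patients)

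*SAP*

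**What the plan says.** Four places in the SAP bear on the death criterion.

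- **11a (event rates):** "All-cause death rates were assumed to be 2.0% with upper 95% CI of 4% in 400 patients".
- **26a (outcome definitions, safety):** the absolute risk of death should not "fall outside the upper 95% CI of 2% per year on trial drugs versus no trial drugs".
- **27a (methods):** the tabulation is described as "Death, including fatal haemorrhage, aiming for less than outside the upper 95% CI of 2% per year".
- **Table 2 (feasibility measures):** the Metric column gives <2% for death, next to an empty Achieved cell. The other filled metrics in that column are targets as well: 400 patients, >95%, >=75% and 40-50%. The recruitment row already shows 363 of 400.

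The protocol agrees with 26a. Section 2.2.2 says death "will not differ significantly (ie fall outside the upper 95% CI) from 2% per year on trial drugs versus no trial drugs", and section 9.1 says "We expect deaths including vascular deaths of median 2.0% p.a., with 4% being the upper 95% CI of 2% in 400 patients".

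SAP 4c deals with differences between the protocol and the SAP: "the SAP will take precedence". On interim decisions, 13c says "There are no formal stopping rules".

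**The concern.** The Table 2 cell uses the expected death rate as the ceiling. The text uses the upper confidence limit around that rate, about twice as high. Both cannot be the pre-specified criterion. If the cell is shorthand for the 26a rule, no passage says so, and 4c cannot settle a difference inside the SAP.

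Two further points are open. The 27a phrase runs together being below a limit and lying outside it, so it cannot be applied as written. And the 4% is derived for all 400 patients, whereas 26a speaks of trial drugs versus no trial drugs; neither the group nor the interval method is stated.

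At stake is the safety statement the trial reports. The expected number of deaths lies right beside the range in which the two criteria give opposite answers, so the conclusion could turn on a choice made after the deaths are known. SAP 13a provides for provisional data to be tabulated and analysed for the oversight committees at a soft lock, so deaths may be seen before final lock.

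**Working it through.** **Inputs.** Expected death rate 2.0% and upper limit 4% in 400 (SAP 11a, protocol 9.1); N = 363 recruited (SAP Table 2), or 400 planned; one-year follow-up (SAP 9), so the annual rate is read as the trial proportion. Assumptions: vital status known for everyone, no drug effect, deaths binomial.

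**1. Reproduce the plan's 4%.** Upper two-sided 95% limit for 8 deaths in 400 (2.0%):

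- Exact (Clopper-Pearson): 3.90%
- Wilson: 3.90%
- Wald: 2% + 1.96 × √(0.02 × 0.98 / 400) = 2% + 1.37% = 3.37%

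The exact and Wilson limits round to the stated 4%; Wald does not.

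**2. Turn each criterion into a count at N = 363.**

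- <2%: 0.02 × 363 = 7.26, so at most 7 deaths (7/363 = 1.93%; 8/363 = 2.20%).
- 4% limit: 0.04 × 363 = 14.52, so at most 14 deaths (14/363 = 3.86%; 15/363 = 4.13%).

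The criteria disagree at 8 to 14 deaths. The expected count is 7.3. At N = 400, <2% also allows 7 (8/400 is exactly 2%), the 4% limit allows 16, and the disagreement range is 8 to 16.

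**3. Probability of disagreement at a true 2.0%**, P(X ≤ upper count) − P(X ≤ 7):

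| N | P(X ≤ 7) | <2% missed | P(X ≤ upper count) | Disagree |
|---|---|---|---|---|
| 363 | 0.5596 | 44.0% | 0.9928 (14) | 43.3% |
| 400 | 0.4515 | 54.9% | 0.9966 (16) | 54.5% |

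At N = 363 the 4% limit is missed in 0.7% of trials (1 − 0.9928).

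**4. Interval method and group (true 2.0%).**

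- N = 363, limit recomputed for that N: exact 4.03% and Wilson 4.02% still allow 14 deaths, so 43%. Wald, 3.44%, allows 12 and gives 41%.
- One drug's half, n = 181 (assuming all 363 enter that comparison 1:1): <2% allows 3 deaths and is missed in 49.0%. With a fixed 4% limit (7 deaths) the criteria disagree in 46.0%; with that group's own exact limit, 5.26% (9 deaths), in 48.7%.

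**5. True rate (whole trial, N = 363, fixed 4% limit).**

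| True rate | Disagree |
|---|---|
| 1.0% | 3% |
| 1.5% | 18% |
| 2.0% | 43% |
| 2.3% | 57% |
| 2.5% | 65% |

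The 2.3% row is the sum of the vascular (1.8%) and non-vascular (0.5%) death entries in SAP Table A. It is a sensitivity case only: the protocol describes the same entries as means ("We calculated mean annual event rates (Table 6) from trials"), while its 2.0% is called a median.

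**The case against.** The strongest counter-argument is that 43% depends on how an unclear sentence is read. If the intended rule were that the upper 95% limit of the observed rate must stay within 4%, then at N = 363 seven deaths pass (exact limit 3.93%) and eight fail (4.30%). That is the same cut as <2%, and the conflict disappears. At N = 400 that rule would allow 8 deaths against 7, so the two would differ only at exactly 8 deaths, in 14% of trials. But 26a, 27a and protocol 9.1 all refer to the limit of 2%, and 11a defines the 4% that way. The observed-rate reading is not what is written. That the wording leaves room for it, with the allowed deaths at N = 363 falling from 14 to 7, is a further reason to fix it.

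Second, Table 2 abbreviates elsewhere: its recruitment metric omits the 24-month window. The cell may therefore be a drafting slip rather than a rival rule. That is plausible, but it is the figure a reader will set beside the achieved rate, and it would show a missed target in 44% of trials running exactly as planned.

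Third, the disagreement shrinks if the true death rate is lower: 18% at 1.5% and 3% at 1.0%. This stands and limits the size of the problem.

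Fourth, the consequence is modest. Death is a secondary outcome, no stopping rule rests on it, and Table 2 will print the number and percentage of deaths. Table 3 and the serious adverse event tables give deaths or fatal events by group. This also stands. It limits the effect to the met-or-missed statement without removing the contradiction.

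**Conclusion.** The inconsistency is real and should be fixed. The SAP contains two thresholds for one pre-specified safety criterion, a factor of about two apart, and no text chooses between them. Under the plan's own 2.0% rate, with 363 patients, a whole-trial denominator, a fixed 4% limit and no drug effect, they give opposite answers in 43% of trials. Changing the interval method or applying the rule to one drug's half moves this only between 41% and 49%. It depends more on the true death rate (3% at 1.0%, 65% at 2.5%) and on taking the text at its word that the limit belongs to 2%. The effect is confined to the reported safety conclusion; the planned comparisons of death between groups are untouched.

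**What to change.** Before database lock, and preferably before the soft-lock review in 13a:

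1. Reconcile Table 2, 26a and 27a to one death criterion in the same words, replacing the <2% cell with the rule the investigators confirm from 26a.
2. State the group it applies to: the whole trial, or on drug versus no drug.
3. State the interval method. The 4% in 400 matches an exact or Wilson limit (3.9%), not Wald (3.4%).
4. Report each allocated group's death rate with its own 95% confidence interval beside the comparisons already planned in 27a.
5. Add a note that 4% expresses the precision available with all 400 patients and does not by itself show either drug to be safe.

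The cost is SAP wording only: one table cell, two bullets, and a sentence or two on group, interval method and interpretation. Data collection, sample size and planned comparisons do not change.
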